8.1.3 Other study parameters

Mediators

T0, T1, T2, T3, T4, and 1-year follow-up measures (girls)

Self-reported trait mindfulness

Self-reported trait mindfulness will be assessed using the Mindful Attention Awareness Scale-Adolescents (MAAS-A) (Brown, West, Loverich, & Biegel, 2011) and the Child and Adolescent Mindfulness Measure (CAMM) (Greco, Baer, & Smith, 2011). The MAAS-A comprises a single scale with 15 items rated on a 1–6 Likert scale, providing a single score to represent dispositional mindfulness. Test-retest reliability for the MAAS-A has been found to be moderate in adolescent samples over 3- and 10-month periods ($r = 0.35\text{--}0.52$; Black et al., 2012). The study will use the Dutch translation of the 10-item CAMM (de Bruin et al., 2014), which proposes a two-factor structure: (1) Present moment, non-judgmental awareness; and (2) Suppressing or avoiding thoughts and feelings/distractibility or difficulty paying attention. However, the second factor has shown lower internal consistency in Dutch studies ($\alpha = 0.58$ and $\alpha = 0.50$). Reported internal consistencies of the CAMM and its subscales are generally lower than those of the MAAS-A but remain acceptable in most studies ($\alpha = 0.70\text{--}0.85$). An exception is a study by Noggle and colleagues (2012), which reported poor internal consistency ($\alpha = 0.58$). Test-retest reliability data for the CAMM in intervention-focused studies are unavailable. However, findings by de Bruin and colleagues (2014) consistently indicate

that the second factor (suppressing or avoiding thoughts and feelings/distractibility or difficulty paying attention) has lower internal consistency compared to the first factor.

Self-reported emotion regulation

Self-reported emotion regulation will be assessed using the Dutch version of the Difficulties in Emotion Regulation Scale (DERS; Gratz & Roemer, 2004; Neumann, van Lier, Gratz, & Koot, 2010). The DERS is a 36-item self-report questionnaire designed to evaluate individuals' ability to identify, understand, and manage their emotions (Gratz & Roemer, 2004). The scale comprises six subscales: Lack of Emotional Awareness (6 items), Lack of Emotional Clarity (5 items), Difficulties Controlling Impulsive Behaviors When Distressed (6 items), Difficulties Engaging in Goal-Directed Behavior When Distressed (5 items), Nonacceptance of Negative Emotional Responses (6 items), and Limited Access to Effective Emotion Regulation Strategies (8 items). Each item is rated on a 5-point Likert scale ranging from 1 (almost never) to 5 (almost always). Subscale scores will be calculated by summing the corresponding items. The subscales of the Dutch version of the DERS have demonstrated satisfactory to high reliability, with Cronbach's alphas ranging from 0.72 to 0.87 (Neumann et al., 2010).

Implementation measures

T1, T2, T3, T4

In order to study how implementation impacts the hypothesized effects of the Girls United program, the following variables will be studied:

- (1) *Program dosage*, i.e., how much of the program has been followed, will be measured by the total amount of complete delivered training sessions within each dyad (one question) and the percentage of dyadic attendance to the sessions (one question). Data on both variables will be collected by the trainers, who will have to fill out a digital form after each training session.
- (2) *Participant responsiveness*, i.e., the degree to which the program engages and stimulates the interest of the participants, will be measured by seven questions assessing rates of usefulness, perceived benefits, engagement, enjoyment, helpfulness, intentions to apply to daily life, and perceived success in applying to daily life. Girls will be asked to rate their answers on a 5-point Likert scale, ranging from "not at all" to "very much." Data will be collected by digital questionnaires immediately following each training session.
- (3) The extent of participants' self-reported practice outside of the training sessions will be measured by the percentages of (1) completed activities (i.e., back-end data collected by the app), (2) completed daily state mood monitoring activities (i.e., back-end data

collected by the app), and (3) completed daily mindfulness-based questions (i.e., back-end data collected by the app). Moreover, data on self-reported practice outside of the training sessions will be collected by asking girls to fill out digital questionnaires after each training session about the amount of self-reported mindfulness practices within their dyadic conversations, ranging from low [once a week or less], medium [three times a week or less], and high [at least three times a week].

- (4) *Program fidelity*, i.e., the extent to which the delivered program corresponds to the original program will be collected using self-administered digital forms completed by the trainers after each lesson, reporting whether the scheduled activities were delivered (yes or no) and whether the trainers (yes or no) altered any activities. The fidelity forms will list all activities planned for each training session, based on the training manual. Each item will have data on the percentage of activity completeness (i.e., the numerator will be the number of activities delivered, and the denominator will be the total number of activities planned), and percentage of alterations (i.e., the numerator will be the activities instructors reported changing, and the denominator will be the number of activities planned). A fidelity variable for each dyad will be calculated as follows: $\text{fidelity} = \% \text{ completeness} \times (1 - \% \text{ alteration})$. Dyads will then be divided into two groups according to the level of fidelity: those that received $\geq 80\%$ of the proposed activities will be considered to have completed the program, whereas those that received $< 80\%$ of the activities will be considered to have incomplete implementation.
- (5) *Treatment contamination*, i.e., monitoring of the control group, will be measured by an online questionnaire for parents at T0, T2, and T4 with one question: “Did your child attend a mindfulness-based course in the last two or three months, and if yes, please mention the name of the course.”

Trainer measures

T1, T2, T3, T4

These following variables will be measured among the trainers for every dyad: Trainer Coping with Occupational Stress tied to the Context in which they implement the Program will be measured at the end of each lesson of the prevention program, Self-Reported Teaching Competence, Self-Reported Competence Teaching the Course in the Future, Trainers Program Expectations will be assessed at the end of each phase of the prevention program.

Trainers Coping with Occupational Stress tied to the Context in which they implement the Program

Trainers Coping with Occupational Stress tied to the Context in which they implement the Program will be measured using two items adapted from a study by Braun and colleagues (2024). First item, "To what extent did you find this lesson stressful", will be scored on a dichotomous scale (0 = not stressful, 1 = very stressful). Second item, "How effectively were you able to manage the stress you experienced during this lesson", will be rated with two options (0 = not at all well, 1 = very well)

Self-Reported Teaching Competence

Teaching the course will be assessed using a single-item originally designed for a study by Braun and colleagues (2024), "How competently do you feel you delivered the course?". This item will be rated on a 9-point Likert scale ranging from 1 (not at all competently) to 9 (very competently).

Self-Reported Competence Teaching the Course in the Future

Trainers' confidence teaching the course in the future will be measured using a single-item originally designed for a study by Braun and colleagues (2024), "How confident would you feel teaching the course again?" The item will be rated on a 9-point Likert scale ranging from 1 (not at all confident) to 9 (very confident).

Trainers Program Expectations

Trainers' expectations about the program will be assessed using an adapted version for this study derived from the Credibility/Expectancy Questionnaire (Borkovec & Nau, 1972). This 5-item measure evaluate the the degree to which trainers believe that the intervention is credible and effective in improving outcomes (e.g. "How important do you think it is to make this training available to other girls?"). Item scores ranged from 1 (not at all) to 9 (very). This measure has demonstrated a strong reliability ($\alpha > 0.80$ for original measure (Deville & Borkovec, 2000).

Descriptives

Age (based on date of birth) and gender (male or female) will be registered on the completed participant informed consent forms and this will be checked by the trainers.

T0 measure (parents/main caretakers)

Socioeconomic status

Parental education level will be used as an indicator of socioeconomic status (SES), which has been regarded the most powerful indicator of SES (Davis-Kean, Tighe & Waters, 2021; Tighe & Davis-Kean, 2021; Waters, Ahmed, Tang, Morrison, & Davis-Kean, 2021). To this end, the primary caregiver will report the education level of the mother and the father of each participant. Educational levels will be rated according to the Dutch Standard Education Classifications (Statistics Netherlands, 2021), which corresponds to the International Standard Classification of Education (ISCED; UNESCO, 2011). Following the ISCED classifications, parental education levels will be coded using an 8-point scale, with education levels including the following: 0 = no education/early education, 1 = primary education, 2 = lower secondary education (e.g., junior secondary school, middle school, junior high school), 3 = upper secondary education (e.g., senior secondary school, [senior] high school), 4 = post-secondary non-tertiary education (e.g., technician diploma, primary professional education), 5 = short-cycle tertiary education (e.g., [higher] technical education, higher/advanced vocational training, associate degree), 6 = bachelor's degree or equivalent, and 7 = master's degree, equivalent or higher. Parental education level will be based on the highest completed parental education level per household. That is, if a child has one parent with upper secondary education (i.e., 3) and another parent with a bachelor's degree (i.e., 6), then we will code this child's parental education with bachelor's degree (i.e., 6).

Intervention status will be dummy-coded (0 = control, 1 = Girls United program) and registered by the research assistants in a password protected access file.

T0 measure (trainers)

At baseline these following variables will be measured among trainers:

Qualifications trainers

The trainers' qualifications pertain to their competency in teaching mindfulness and their personal meditation practice. These qualifications will be evaluated through four questions: (1) whether the trainer holds a certification as a mindfulness trainer or as a mindfulness coach for children/adolescents, (2) whether they have completed formal mindfulness training programs, and if so, which ones, (3) the frequency of their meditation practice (e.g. daily, multiple times daily, or weekly on average, and (4) the duration of their meditation sessions (e.g., half an hour or less, half an hour to an hour, or more than an hour).

Trainers General Levels of Self-Reported Global Perceived Stress

Trainers' stress will be measured using 10 items from the *Perceived Stress Scale* (Cohen et al., 1983). Items (e.g., "In the last month, how often have you found that you could not cope with all the things that you had to do?") will be rated on a 5-point Likert scale (1 = never, 5 = very often; $\alpha = 0.85$). Reverse scoring is applied to specific items as needed, so that higher scores reflected greater levels of stress. Research on the psychometric properties of this scale in various populations has demonstrated to have an adequate reliability (> 0.70) and validity as it is correlated with related experiences of depression and anxiety symptoms, among others (Cohen et al., 1983; Lee, 2012).

Demographics

Gender will be assessed using a binary scale (0 = male, 1 = female), and age will be measured in decades with the following categories: 1 = 20-30 years, 2 = 31-40 years, 3 = 41-50 years, 4 = 51-60 years, and 5 = 61 years of older.

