3. STUDY DESIGN

Design

The Girls United cRCT aims to evaluate the effectiveness of the Girls United program, a school-based intervention blending targeted mindfulness and psychoeducation. Delivered by trained and experienced mindfulness health professionals, the program is compared to a teaching-and-care-as-usual (TAU) approach. The study includes two groups: (1) an intervention group where girls' friendship dyads participate in the Girls United program, and (2) a control group where girls' friendship dyads receive TAU.

Duration

The 14-week Girls United program will be delivered in two cohorts across two academic years: cohort 1 in 2025–2026 and cohort 2 in 2026–2027. The program will run in four phases from October 2025 to May 2026 for both cohorts. Baseline measurements (T0) will occur in September 2025 for cohort 1 and February 2026 for cohort 2. Subsequent measurements include T1 (November 2025 for cohort 1 and April 2026 for cohort 2), T2 (January 2026 for cohort 1 and June 2026 for cohort 2), T3 (March 2026 for cohort 1 and October 2026 for cohort 2), and T4 post-intervention measurements (May 2026 for cohort 1 and December 2026 for cohort 2). A long-term follow-up measurement (T5) will be conducted in May 2027 for cohort 1 and December 2027 for cohort 2 (see Figure 1).

Setting

The study will take place at mainstream primary schools of school partnerships such as RiBA, BLICK op onderwijs and Scholennetwerk BSI and schools that are involved via our social media channels and webinars. These schools will be broadly representative of Dutch mainstream primary schools with respect to the type of school (urban/rural, large/small) and high/middle/low Socio Economic Status (SES) of the school.

[figure not shown]

Figure 1. Flowchart of study assessment time points for cohort 1 and 2.

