4.3 Exclusion criteria

Exclusion criteria at *participant/girl* level:

- 1) Following and/or participating in an another individual or group-based mindfulness-based training in academic year 2025/2026 or 2026/2027.

Exclusion criteria at the *school* level (to mitigate any risk of difficulties in trial implementation):

- 1) Not having a headteacher in academic year 2025/2026 or 2026/2027.
- 2) Judged as 'inadequate' during the most recent school inspection by the Dutch Inspectorate of Education.
- 3) Implementing another mindfulness-based intervention in academic year 2025/2026 or 2026/2027.

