8.2 Randomisation, blinding and treatment allocation

Dyads will be randomly assigned in a 1:1 ratio to either the intervention group (max 80 dyads; $n = \text{max } 160$ girls) or the control group (TAU; max 80 dyads; $n = \text{max } 160$ girls) by an independent researcher using CASTOR EDC, a web-based randomization program compliant with Good Clinical Practice (GCP) guidelines. Ideally, randomization will occur on a single day after completing the screening phase. If this is not feasible (e.g., due to time constraints), randomisation will proceed in batches of 50 dyads (100 girls) and on classroom level. The median of the screening scores will be calculated, and dyads where one or both girls above the median will be included. These dyads will then be randomly assigned to the intervention or control group using a block randomisation procedure (50% allocated to each group). Allocation will be concealed through a computer-generated list in a secure web-based application. However, due to the organisational structure of the prevention program, participants, parents, schools, and researchers will be aware of group assignments. As the trial follows an open-label design, unblinding will not occur.

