8.3 Study procedures

Measures

Questionnaires T0, T1, T2, T3, T4 and one-year follow-up T5

For the dyad girls, filling out the T0 questionnaires will take place via BigBlueButton, so that the girls the first time that they have to fill out the questionnaires will be able to ask questions about the items and the researchers will be able to assist. Both girls of a dyad will receive a link to the BigBlueButton environment via email. Via BigBlueButton it is possible to deliver the questionnaires via the chat-function. Both girls of a dyad will fill out their own questionnaires independently.

Girls, parents/main caretakers, and trainers will receive online questionnaires via email at the follow-up timepoints (T1, T2, T3, T4), and one-year follow-up (T5). A trained PhD student or senior research assistant will be responsible for distributing all questionnaires via Qualtrics. If participants do not respond within one week, a reminder email will be sent. Three days later, those who still have not completed the questionnaire will receive a follow-up phone call from the trained PhD student or senior research assistant. Teacher-mentors will assist by sending the reminder emails, while the trained staff will handle the phone calls. The estimated time burden for completing the questionnaires is detailed in Table 1 for girls, Table 2 for parents/main caretakers, and Table 3 for trainers.

Table 1. Specified duration: girls.

Questionnaire	Duration (min)
Screening	
Co-rumination Questionnaire – CRQ short	2
Total	2
T0 t/m T4 and follow-up primary outcome measures	
Co-rumination Questionnaire – CRQ short	2
Total	2
T0 t/m T4 secondary outcome measures	
RCADS (Subscale Generalized Anxiety Disorder)	2
CDI-2	10
PANAS-C	5
CoDEQ	5
NRI	10
CBSK	6

Total		38
T0 t/m T4 and follow-up: moderator		
Total		2
T0 t/m T4 and follow-up: mediators		
MAAS-A		5
CAMM		5
DERS		10
Total		20
T1 t/m T4 implementation variables* only for girls in the intervention condition		
Participant responsiveness		14
Practice outside of the training session		7
Total		21.5
Total Screening (min.)		2
Total T0 t/m T5 (min.)	60 x 6 =	360
Total implementation measures. only for girls in the intervention condition (min)		21.5

Table 2. Specified duration: parents/caretakers.

Questionnaires	Duration (min)
T0	
Descriptives (SES)	2
Total	2
T0 en T4	
Parental health care use of their child/family	3
Total	3
T0, T2 en T4 : Implementation variables	

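### The control-group contamination question looks back two or three months but is asked four to six months apart, leaving a 3–4 month blind stretch in cohort 2 that could hide a whole course

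*Protocol*

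**What the plan says.** Section 8.1.3 lists treatment contamination as the fifth implementation measure and describes it as monitoring of the control group. It "will be measured by an online questionnaire for parents at T0, T2, and T4 with one question", worded as "Did your child attend a mindfulness-based course in the last two or three months", with a request to name the course. Table 2 in section 8.3 repeats the schedule ("T0, T2 en T4 : Implementation variables") and allots the item one minute.

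Section 3 dates the three waves:
- T0: "Baseline measurements (T0) will occur in September 2025 for cohort 1 and February 2026 for cohort 2".
- T2: "T2 (January 2026 for cohort 1 and June 2026 for cohort 2".
- T4: "T4 post-intervention measurements (May 2026 for cohort 1 and December 2026 for cohort 2".

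No other item asks about mindfulness courses during follow-up. The parent question on health care use (section 8.1.2) concerns care for psychosocial, emotional or behavioural problems. Sections 4.3 and 5.1 set rules on other mindfulness programmes but do not measure exposure.

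**The concern.** A repeated question covers follow-up fully only if each look-back reaches the previous asking. Here the look-back is shorter than every interval between askings, so part of each interval is never asked about. The phrase is also ambiguous: one parent may think back two months and another three.

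The item is the plan's only direct record of whether control girls took a mindfulness course elsewhere. If a course can fall wholly between two windows, the trial may report less contamination than occurred. A small difference between the arms would then be harder to interpret.

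**Working it through.** The plan states no coverage figure, so there is none to reproduce. The check is calendar arithmetic on the month-level dates in section 3, taken as printed.

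**Step 1. Intervals between askings.**
- Cohort 1: September 2025 to January 2026 = 4 months; January to May 2026 = 4 months.
- Cohort 2: February to June 2026 = 4 months; June to December 2026 = 6 months.

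**Step 2. Unasked share of each interval** = (interval − recall) / interval.

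| Interval | 3-month recall | 2-month recall |
|---|---|---|
| 4 months | (4 − 3)/4 = 25% | (4 − 2)/4 = 50% |
| 6 months (cohort 2, T2–T4) | (6 − 3)/6 = 50% | (6 − 2)/6 = 67% |

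**Step 3. Unasked share over T0–T4.**
- Cohort 1: (1 + 1)/8 = 25% to (2 + 2)/8 = 50%.
- Cohort 2: (1 + 3)/10 = 40% to (2 + 4)/10 = 60%.

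**Step 4. From calendar time to courses missed.** The question asks whether the child attended a course within the window, so any course that overlaps the window is reportable. A course is missed only if it starts and ends inside the blind stretch. With start dates spread evenly over the interval, the share missed = (blind stretch − course length) / interval, or zero if the course is longer than the blind stretch.

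The plan gives no course length for outside programmes. I assume 8 weeks, the length of the course that the trainers themselves followed (section 5.1), and convert months to weeks.

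| Interval | Recall | Blind stretch | Share missed |
|---|---|---|---|
| 4 months (17.4 weeks) | 3 months | 1 month (4.3 weeks) | 0% |
| 4 months (17.4 weeks) | 2 months | 2 months (8.7 weeks) | (8.7 − 8)/17.4 = 4% |
| 6 months (26 weeks) | 3 months | 3 months (13 weeks) | (13 − 8)/26 = 19% |
| 6 months (26 weeks) | 2 months | 4 months (17.4 weeks) | (17.4 − 8)/26 = 36% |

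**Range.** For very brief exposures the missed share approaches the calendar shares in step 2. A course longer than 17.4 weeks could not fall wholly inside any of the blind stretches.

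**Where the blind stretch falls.** In cohort 2 the December 2026 question reaches back to September or October, so the time from June until then is not covered.

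**The case against.** The strongest case against is that this is a minor wording mismatch in one implementation item. Much of that stands. Reportable overlap brings the loss in cohort 1 close to nil for an 8-week course, and the mismatch matters mainly in one interval of one cohort. No analysis in section 10 uses the item. Trait mindfulness (MAAS-A, CAMM) and emotion regulation (DERS) are measured in the girls at every wave, so a rise in the control arm would give indirect evidence of exposure. It would therefore be too strong to say that dilution could not be detected at all. What these points do not remove is the gap itself: indirect scores do not show whether a girl attended a course, and no other item does.

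A reader might go further in four ways that the documents do not support.
- **That two thirds of the whole exposure period is missed.** That figure is the worst single interval under the shorter reading of the look-back. Over T0–T4 the range is 25–60% across the two cohorts.
- **That the wording weakens the expected effect or the power.** Contamination could do that, but the documents give no contamination rate, and rewording the question would not change how many control girls are exposed.
- **That the item fails as a check on eligibility.** Section 4.3 excludes girls in another "individual or group-based mindfulness-based training in academic year 2025/2026 or 2026/2027", a longer span than the question covers. But section 8.1.3 presents the item as monitoring of the control group, and nothing says that it enforces the exclusion.
- **That both arms share schools, so exposure through classmates goes unrecorded.** Section 8.2 says "Dyads will be randomly assigned in a 1:1 ratio", and section 4.2 requires the two friends of a dyad to attend the same school. Mixing of arms within a school is a plausible inference but is not stated, and section 8.2 also foresees randomisation at classroom level if batches are needed.

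**Conclusion.** The point holds in limited form. The look-back does not reach the previous asking in any interval: 25–50% of each 4-month interval and 50–67% of cohort 2's T2–T4 interval go unasked. The practical weakness is the 3–4 month blind stretch in cohort 2, where roughly a fifth to a third of 8-week courses (19–36%) would go unreported. In the 4-month gaps it is about 0–4%.

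The calendar shares rest only on the printed dates, which are by month, so each interval is uncertain by up to about a month. The shares of courses missed rest also on the assumed 8-week length, evenly spread start dates and accurate recall by parents. The consequence is for describing and interpreting the control condition; the primary test is unaffected. It is worth correcting because the correction costs almost nothing and a missed period can later be recovered only by longer recall.

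**What to change.** At T2 and T4, replace the two-or-three-month phrase with *since the previous questionnaire*, with the date of that questionnaire filled in. This leaves none of T0–T4 unasked and removes the ambiguity of the present wording.

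Leave the T0 look-back no shorter than it is now. Tying it to the start of the school year could shorten it for cohort 1, whose T0 is in September: if the year begins in August or September (an assumption, since the plan gives no date), it would reach back only weeks.

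Keeping the present wording and asking at every wave from T0 to T4 is less good. Cohort 1's gaps would all be 2 months and fully covered. Cohort 2's would be 2, 2, 4 and 2 months, leaving 1 to 2 of 10 months (10–20%) unasked between June and October 2026, and it would need two more parent contacts.

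A tick-box on contact with programme material through a classmate is optional. It addresses a separate route, and naming the app to control families might itself prompt interest.

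The cost is one changed phrase in a one-minute parent item, and a recall period of 4 to 6 months instead of two or three. The change covers T0–T4 only; the question is not asked at T5.
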